5.0 DATA COLLECTION AND MANAGEMENT

5.1 DATA PROCUREMENT

- Recruitment information will be procured through physician referral, or through review of an existing daily EPIC workbench report* of opioid and alcohol misuse.
- Administrative outcomes will be procured through a monthly EPIC report.**
- Patient Baseline Survey Measures will be procured through patient interviews and will be recorded on a tablet or computer into a web-based survey system (REDCap).
- Some demographic and all diagnosis variables will be procured from eligibility screener conducted in REDCap. (Eligibility screener variables from all patients that screen will be used to assess study feasibility. Data from patients not enrolled in the study will be anonymous, i.e., they will not be linked to an MRN or any identifying information.)
- Patient Follow-up Survey Measures will be procured through a telephone interview by 1-month after the patient is discharged from the hospital. During collection of contact information at the baseline visit, patients may opt-in to receive text message reminders about this interview. These reminders will be sent via Twilio SMS through REDCap and will not contain any identifying information regarding the patient or the specific study.
- Provider Survey Measures will be procured through provider interviews and will be recorded and transcribed.

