Past 30-day frequency of heavy drinking days and/or all days of any opioid use	Days of use in the past 30 – Adapted National Survey of Drug Use and Health (NSDUH) ⁵⁸ (Continuous)	Baseline interview 1-month interview
Secondary Exploratory Outcome		
90-day readmission to CSMC	Readmitted to CSMC up to 90-days after discharge during study period	CSMC admin data
Covariates		
Sociodemographics	Gender, sex, age, race/ethnicity, income, education, occupational status, marital status, zip code, homelessness in past six months.	Eligibility screener; Baseline interview
OAUD diagnosis	Moderate or Severe, ASSIST ⁴⁵	Eligibility screener
Pain Level	Pain level between 1-10; Pain interference level between 1-10, PEG ⁵⁶ (Continuous)	Baseline interview 1-month interview
Primary and secondary diagnosis (inpatient stay)	Medical or mental health conditions as determined by the inpatient physician (Categorical)	CSMC admin data
Length of hospital stay	Number of days of hospital stay (Continuous)	CSMC admin data
Intervention “dose”; exposure	Amount time spent with patient (Continuous)	START Registry
Insurance	Payer name	CSMC admin data

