****Monthly EPIC Report Elements**

- Demographics: MRN; Age; Age at encounter; Date of Birth; Sex; Race; Ethnicity; City; Zip Code
- Hospital encounter data: Type; Dates; Disposition; Attending provider; PCP; Psychiatry consult;
- Diagnoses during encounter: ICD 10s: F10-F19; Problem list items
- CIWA Protocol and measure information
- Inpatient and discharge medication information: Suboxone; Buprenorphine; Subutex; Methadone; Naltrexone; Naloxone; Disulfiram; Acamprosate; Topiramate; Gabapentin; Narcan; Naloxone.
- Lab results: AST; ALT; GGT; Urine Toxicology Screen; Blood Alcohol Level
- Flowsheet Data: RN Alcohol Screening Questions
- Social History: Tobacco usage; Alcohol usage; Drug usage
- Family history of substance use disorder
- Notes: Physician, Nursing and Allied health Professional documentation
- Hospital Utilization Metrics: Length of Stay; Inpatient admissions in prior 12 months; ED admissions in prior 12 months; Number of 30-day readmissions

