7.0 STATISTICAL CONSIDERATIONS

7.1 STUDY OUTCOME MEASURES

Although we do not anticipate that this pilot study will be sufficiently powered to detect treatment effects, we will estimate models with the primary goals of learning the variance of the treatment effect estimator, which will be used in power calculations for future study design, and detecting areas of potential concern. This model would look for differences in outcomes between intervention (START) and control (UC) conditions, controlling for baseline measure of the outcome, where appropriate, using a generalized linear modeling-based framework. For dichotomous outcomes, we will employ a logistic regression model of the form $Pr(yyii = 1) = 1/(1 + \exp(-(\beta\beta_0 + \beta\beta_1xxii + \beta\beta_2zzii)))$. Here i indexes individuals, $\beta\beta_0$ represents the overall intercept, $xxii$ represents the treatment status of individual i , 0 for control, and 1 for intervention, and $\beta\beta_1$ is the effect of the intervention. The variable $zzii$ represents the baseline measure and $\beta\beta_2$ associated coefficient. Continuous outcomes will be modeled using linear regression. We will also perform exploratory analyses to investigate whether there are subgroups that may be responding better or worse to the intervention by interacting the covariates in Table 2 with the treatment indicator. Because there will be nearly as many potential covariates as observations, we will employ the “horseshoe prior” in Bayesian analyses of the outcome.⁶⁴ Qualitatively, this model starts from the assumption that most (if not all) of the covariates are unimportant for predicting the outcome, and attempts to learn which covariates are important. The intention is not so much to detect significant differences, but rather to highlight areas of potential concern. For example, if individuals with high pain levels respond less well to START recipients, this exploratory approach could draw attention to potential issues that could be optimized ahead of a future trial.

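### No baseline term is named for 90-day readmission, although prior-12-month admissions are in the monthly EPIC report and could serve

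*Combined protocol and SAP*

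**What the plan says.** Section 7.1 gives one modelling rule for all outcomes: treatment arms are compared "controlling for baseline measure of the outcome, where appropriate, using a generalized linear modeling-based framework". For binary outcomes, "For dichotomous outcomes, we will employ a logistic regression model of the form" shown there: an intercept, a treatment indicator and one further term z, described as the baseline measure. Its coefficient on treatment is called the effect of the intervention. The models serve the "primary goals of learning the variance of the treatment effect estimator, which will be used in power calculations for future study design", and to flag areas of concern. The pilot is not expected to be powered for treatment effects.

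The outcome table in section 5.3 lists 90-day readmission as a secondary exploratory outcome, defined as "Readmitted to CSMC up to 90-days after discharge during study period" and taken from hospital administrative data. The covariates in that table are sociodemographics, OAUD diagnosis, pain, inpatient diagnoses, length of stay, intervention dose and insurance. Earlier admissions are not among them.

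Section 5.1 states that "Administrative outcomes will be procured through a monthly EPIC report". The elements of that report include "Hospital Utilization Metrics: Length of Stay; Inpatient admissions in prior 12 months; ED admissions in prior 12 months; Number of 30-day readmissions". Section 2.0 assigns the test of 90-day readmission to a larger, later study.

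**The concern.** The adjustment rule works for days of use, which are measured at baseline and at one month. It gives no instruction for readmission. Everyone is an inpatient at entry, so there is no baseline readmission status to put in z. Read literally, z drops out; read generously, the analyst chooses something. The protocol does not say which.

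Two things are at stake. First, a plausible prognostic variable in the planned extract may go unused on the outcome that the larger study will test. Second, a stated goal of the models is a variance for later power calculations. For readmission, that variance depends on what z is and on the effect scale, and neither is fixed.

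The report also gives no reference date for its 12-month look-back. A count that ran past the index admission could include the index stay, or the readmission being modelled.

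**Working it through.** **1. The plan's own figures.** 16 patients per month × 5 months = 80 = 2 × 40, as stated in section 7.2. The documents give no readmission rate, precision or power for this outcome, so there is nothing further to reproduce.

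**2. Unadjusted precision at 40 per arm.** With the same rate p in both arms (assumed), SE of the risk difference = √(2p(1−p)/40).

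| p (assumed) | SE | 95% half-width (1.96 × SE) |
|---|---|---|
| 20% | 0.089 | 17.5 points |
| 30% | 0.102 | 20.1 points |
| 40% | 0.110 | 21.5 points |

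**3. Adjusted, risk-difference scale.** Trials of 80 patients were simulated with prior admissions coded 0/1/2/3+ (splits such as 50/25/13/12% or 50/25/15/10%, assumed) and about 30% readmission overall, with a risk difference of about −8 points (for example 26% v 34%, assumed). The adjusted estimate is the standardised difference (1/80) Σ[expit(b0 + b1 + b2·z_i) − expit(b0 + b2·z_i)]; the unadjusted one is the difference in proportions. Ranges are across runs.

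| Odds ratio per prior admission (assumed) | Variance ratio, adjusted/unadjusted | Worth in patients, 80/ratio − 80 |
|---|---|---|
| 1.0 | 1.01 | −1 |
| 1.2 | 1.01 | −1 |
| 1.5 | 0.96 to 0.99 | 3 to 1 |
| 2.0 | 0.88 to 0.91 | 11 to 8 |
| 2.5 | 0.81 to 0.84 | 19 to 15 |

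The mean estimate was unchanged. A second form of the covariate (standardised log(1 + count), treatment odds ratio 0.5, readmission 20 to 40%, all assumed) gave ratios from 1.01–1.02 with no association to 0.82–0.89 at an odds ratio of 2.5 per SD. Power of the test of b1 moved by about −0.5 to +3 points from a base of 12–29%.

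**4. Adjusted, logistic coefficient (the scale written in 7.1).** In the setting of step 3 with the 50/25/15/10% split, the SE of b1 rose from about 0.504 to 0.523, 0.544 and 0.574 at odds ratios of 1.5, 2.0 and 2.5. At 2.0 the variance ratio is (0.544/0.504)² = 1.17. The same term that cuts risk-difference variance by 9–12% therefore raises log-odds variance by about 17%. This is not lost information: the adjusted b1 is a conditional effect, further from the null than the marginal one, so the two variances belong to different estimands.

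**5. The anchor date.** Section 6.2 has EPIC data exported monthly. Suppose, for illustration, that a report is run four months after discharge and counts back 12 months from its run date. The window then covers the eight months before discharge, so it holds the end of the index stay, and it also covers the whole 90-day outcome period. A count that stops at the index admission date contains neither.

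**The case against.** The strongest objection is that section 7.1 leaves z open rather than excluding it. Prior admissions could be used under its wording, and a team sizing the next trial can compute both variances from data it holds. That stands: the term is unspecified, not ruled out. The baseline survey offers another candidate, self-reported healthcare use related to substance use. Having more than one candidate is a reason to name one.

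It is also fair that this is an exploratory outcome in an unpowered pilot, and that no association is documented. Even at an odds ratio of 2.5, the SD of the risk difference falls only from about 10.2 to 9.2 points against an assumed 8-point effect. Adjustment does not rescue the comparison.

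A reader might go further in four ways that the documents do not support:

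- **That precision is being thrown away.** This needs a fairly strong association, which is not given; with none, adjustment loses about 1%.
- **That the larger, unadjusted variance will be carried forward.** On the plan's logistic scale the unadjusted variance is the smaller one.
- **That the count exists for every patient.** Section 5.3 lists report elements; it states neither completeness nor whether admissions elsewhere are captured.
- **That the count will contain the outcome.** No anchor is stated, but nothing says that the report date is used.

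**Conclusion.** The point holds as a minor one. Section 7.1 does not name z for 90-day readmission, and a suitable variable in the monthly report is absent from the covariate list and lacks an anchor date. At 40 per arm and about 30% readmission, using it would change risk-difference variance by about +1% (no association) to −16% to −19% (odds ratio 2.5 per prior admission). The readmission rate, the spread of prior admissions and the strength of association are all assumptions.

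The firmer consequence does not depend on how large the gain is. A variance for readmission reported without naming z and the scale could mislead the larger trial's power calculation, because adjustment moves it in opposite directions on the two scales when the association is appreciable.

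**What to change.** - **Section 7.1:** for 90-day readmission, set z to the number of inpatient admissions in the 12 months before the index admission date (0/1/2/3+), index stay excluded.
- **Section 5.3:** add this variable to the covariate list with the same anchor date, so that neither the index stay nor a later readmission can enter the count.
- **Reporting:** give the standardised risk difference and its variance from this model, with the unadjusted variance alongside, and state the scale. If the logistic coefficient is also reported, say whether it is adjusted.

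The cost is about one line in each section and one extra variance in the report. The element is already in the planned extract, though its completeness and look-back date should be checked when it is pulled. The statistical downside is about 1% in precision if prior admissions turn out to be unrelated to readmission.

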4.0 STUDY DESIGN AND METHODS

- Eligibility screening - Assessments, demographics (conducted in person or remotely)
- Informed Consent, if eligible (to be obtained in person either on paper or electronically using an approved platform or remotely using an approved platform)
- Enrollment - the CSMC study staff will enroll consented, eligible patients.
- Baseline interview - after enrollment, the CSMC approved study staff will conduct an in-person or remote 30-40-minute baseline interview. Interview data will be recorded on a tablet or computer into a web-based survey system (REDCap). Patients will be compensated with a \$50 Forte payment card (given in person or mailed).
- Randomization - following consent and the baseline interview, the CSMC approved study staff will randomize the patient to the START or UC arm using REDCap.
- All patients will be given patient education materials on alcohol and/or opioid use disorder, as well as harm reduction materials (OUD only). If the visit is remote, the research team will give these materials to a member of the medical team to deliver to the patient or place them in the patient's room.
- 1-month post discharge follow-up interview - the CSMC approved study staff will conduct a follow-up interview by telephone 1-month after the patient is discharged from the hospital. Patients will receive \$50 loaded onto their existing Forte payment card for participation.

The components of the START workflow process are as follows (also shown in Figure 2):

[figure not shown]
1. Triage (Care Manager CM and Addiction Medicine Specialist AMS):
The CM assesses the patient for acute biomedical needs related to the OAUD. The AMS addresses acute biomedical needs (e.g. facilitates withdrawal management).
2. Engage, assess, plan (CM and AMS) (conducted in person or remotely based on circumstances):
3. If there is not an urgent need for medical intervention or after the urgent medical need is addressed, the CM and/or AMS:
 - engages with the patient (CM and AMS)
 - conducts a diagnostic and biopsychosocial assessment (CM)
 - conducts a complete biomedical assessment and addresses comorbidities (AMS)
 - delivers the brief negotiated interview (BNI), an evidence-based intervention, to assess to increase readiness and develops a plan for initiating evidence-based treatment for OAUD (MAT) and/or psychosocial treatment) during and after the hospital stay (CM)
 - ensures the patient understands the follow-up plan and addresses barriers (CM).

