 - (3) Whether a START is feasible and acceptable with in the inpatient medical setting. These knowledge gains will provide invaluable, preliminary information on how to improve the quality of care for hospitalized patients with OAUD and on how to address an unmet need that has severe individual and societal consequences. The knowledge obtained in the study (and even more so in the larger, subsequent RCT) not only will benefit individual patients who participate in the study but also hospitals looking for a pragmatic and feasible way to improve OAUD care. On a societal level, providing a new way to identify and initiate treatment for patients with OAUD could fill a previous unmet need and bring down healthcare costs related to untreated OAUD. We believe that the long-term gains of the study, in terms of knowledge and substantive gains to the community, far exceed any risks for participants.

Table 2: Flowchart of Procedures

Research Procedures	Baseline visit	During course of hospital stay	1-month post-discharge
Eligibility	R		
Informed Consent	R		
Randomization	R		
Sociodemographic Data	R		
Mental health symptoms (PHQ-9, GAD 7); pain (PEG); substance use (WHO ASSIST, NSDUH) consequences of use (SIP-AD), service utilization (NSDUH, GAIN), stigma (SASS)	R		R
Satisfaction with START intervention ^a			R
Medication for alcohol or opioid use disorder ^b		S	
Therapy for alcohol or opioid use disorder ^b		S	
START Addiction Medicine Specialist (AMS) coordinates team-based care ^c		R	R
START Care Manager (CM) ^c coordinates team-based care		R	R

LEGEND

R = Research item/procedure done only for research purposes and covered by the study

S = Standard of care item/procedure that is part of regular care and billed to the patient/insurance

Footnotes:

- a. Only for patients randomized to the START intervention arm of the study.
- b. For both groups: Usual Care and Start intervention. Includes Brief Negotiated Interview and addiction focused discharge planning and follow-up.
- c. The START intervention utilizes established standard-of-care services and procedures (care manager, addiction medicine specialist, medication treatment, therapy, etc.) and helps integrate them into the patient's care in a systematic way. It is this planned coordination and integration that are the intervention, not the services themselves.

- A list of written materials that will be part of the research is included in Appendices - section 8.0 below.

Behavioral Intervention

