5.3 VARIABLES COLLECTED

- The following data points/variables will be collected:

Baseline Measures:

Variable	Source Document
Demographics 
 • Age • Sex (Biological at Birth) • Gender (Identity) • Race/ethnicity • Housing status • Marital status • Income • Education 	Demographics Form
Mental Health Symptoms 
 • Depression • Anxiety 	PHQ-9 survey ^{51,52} GAD 7 survey ⁵³⁻⁵⁵
Pain intensity and frequency	PEG ⁵⁶
Alcohol/Opioid Diagnosis	WHO ASSIST ⁵⁷
30-day Alcohol/Opioid Use: National Survey on Drug Use and Health 30-day use questions	Patient Survey (Adapted from NSDUH ⁵⁸)
SUD Treatment Utilization	Patient Survey (Adapted from NSDUH ⁵⁸)
Healthcare Utilization Related to SUD	Patient survey (Adapted from GAIN ⁵⁹)
Employment	Patient Survey
Negative Consequences	Short Inventory of Problems Alcohol and Drugs (SIP-AD) ⁶⁰
Patient Experience of Stigma	Adapted from Grosso et al. 2019. ⁶¹ Questions to assess stigma experience.
Self- Stigma	Substance Abuse Stigma Scale (SASS) ⁶²
Receipt of START Intervention Components (Patient)	
START Intervention Received (Assessment, Engagement, Treatment/Discharge Planning); Length of Intervention (hours)	START Patient Registry
START Intervention Follow Up Received (Number of follow up calls made)	START Patient Registry

Follow-up Survey Measures (Patient)	
Mental Health Symptoms 
 Anxiety Depression 	PHQ-9 Survey ^{51,52} GAD 7 Survey ⁵³⁻⁵⁵
30-day Alcohol/Opioid Use: National Survey on Drug Use and Health 30-day use questions	Patient Survey (Adapted from NSDUH ⁵⁸)
SUD Treatment Utilization	Patient Survey (Adapted from NSDUH ⁵⁸)
Healthcare Utilization Related to SUD	Patient survey (Adapted from GAIN ⁵⁹)
Negative Consequences	Short Inventory of Problems Alcohol and Drugs (SIP-AD) ⁶⁰
Employment	Patient Survey
Patient Experience of Chronic Illness Care	PACIC ⁶³
Satisfaction with START intervention	Patient Survey
Provider Interviews (Provider)	
Acceptability/feasibility of START Intervention (Provider Interview Guide)	Provider Interview Guide

Outcome Measures:

Outcome	Measure, Assessment (Type of Variable)	Data Source
Primary Outcomes		
In-hospital MAT initiation	Received an OAUD MAT between admission and discharge (Binary)	CSMC admin data
Linkage to follow-up care	Received at least one visit post-discharge for MAT and/or psychosocial care for OAUD (Binary)	Appointment dates 1-month interview

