- It is not feasible to blind the staff to study condition because the study condition requires specific care by the START. While it is likely (and expected) that medical teams will treat patients in both the experimental and usual care (UC) conditions, patients in the START will have an enhanced experience because they (unlike patients in the UC condition) will be receiving START components designed to increase their readiness to take the medication and link to follow-up care. Moreover, the support provided by the START to medical teams for each START patient is the component that we hypothesize will take the burden off of the medical team and increase the likelihood of the patient receiving medication. Even as medical teams become more aware of medication for OAUD and perhaps increase prescribing, we hypothesize that patients whose medical teams receive support for their START patients will still be more likely to receive medication, even if medical teams are aware they can prescribe these medications. Thus, over time, while we might see increased medication initiation for patients in both study conditions, we still hypothesize statistically and clinically significant differences for patients in the CCT group. Nevertheless, we still plan to safeguard against any biases and effects of UC patients receiving the START. The research team will review electronic health record data to determine whether the START AMS or CM accidentally treated UC patients. Further, as part of this developmental study and pilot test, we are carefully assessing whether (and why) contamination occurs and, if it does, we will take additional steps to further safeguard the experimental condition in the future RCT.

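### Section 7.1 takes its subgroup moderators from a table reference that does not fit, and either list it could mean includes values that arise after randomisation

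*Combined protocol and SAP*

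**What the plan says.** Section 7.1 describes two analyses. The main model compares START with usual care (UC) and adjusts only for the baseline value of the outcome, where there is one. A second, exploratory analysis looks for subgroups "by interacting the covariates in Table 2 with the treatment indicator" and uses a horseshoe prior because the potential covariates are nearly as many as the patients. Section 7.1 gives its models two main goals: to learn the variance of the treatment effect estimator, and to spot possible problem areas before the future trial.

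The document has one table with that number, "Table 2: Flowchart of Procedures" in section 4.0. The same section uses that title again under Surveys. The table lists procedures by visit and has no covariate heading. The only list headed Covariates is the last block of the unnumbered outcome table in section 5.3.

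On timing, section 4.0 says that "following consent and the baseline interview, the CSMC approved study staff will randomize the patient". This happens in hospital, so much of the stay may still lie ahead. On contamination, section 7.2 says that the team will review health records to "determine whether the START AMS or CM accidentally treated UC patients", and will also assess why any contamination occurred. On pain, the covariate row reads "Pain level between 1-10; Pain interference level between 1-10" and gives both the baseline and the 1-month interview as sources. Earlier in section 5.3, "Pain intensity and frequency" appears among the baseline measures and not among the follow-up measures. Table 2 shows the PEG pain scale at both times.

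**The concern.** An interaction with treatment shows who responds differently only if the moderator was fixed before treatment was assigned. A value that arises afterwards may itself be a result of START, or may exist in one arm only. Its interaction then does not describe a kind of patient. Section 7.1 contains no rule that limits moderators to values from before randomisation, and the table it cites does not supply one.

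What is at stake is the use made of the subgroup signals. They are meant to show what to change in START before the larger trial. A signal from contact time or total stay could be read as showing that certain patients do badly under START, when it reflects how much START was delivered or what START did to the stay.

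**Working it through.** **Inputs.** 40 patients per arm (section 7.2; 2 x 40 = 80 and 16 per month x 5 months = 80, so the planned size reproduces). The plan states no power target or effect size for this analysis, and none is needed. The two candidate lists come from sections 4.0 and 5.3. Contact-time distributions, the amount of UC contact and the length-of-stay mechanism are assumptions, marked as such.

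**Step 1: the two candidate lists.**

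| Source | Row | Timing |
|---|---|---|
| Table 2, section 4.0 | Satisfaction with START | 1 month, START arm only |
| Table 2 | Medication for alcohol or opioid use disorder | During stay; also a primary outcome |
| Table 2 | Symptom, pain, use, consequence, service-use and stigma scales | Baseline and 1 month |
| 5.3 covariates | Sociodemographics; ASSIST diagnosis | Screener or baseline, so before randomisation |
| 5.3 covariates | Contact time (START Registry) | After randomisation |
| 5.3 covariates | Total length of stay | Complete only at discharge |
| 5.3 covariates | Pain | Baseline and 1 month |
| 5.3 covariates | Inpatient primary and secondary diagnosis | No cut-off; the monthly EPIC report holds diagnoses from the whole encounter |
| 5.3 covariates | Insurance | No date given |

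Of the seven rows in 5.3, two (contact time, total stay) are not fixed at randomisation, two more (pain, inpatient diagnosis) need a timing limit, and insurance needs a date.

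**Step 2: contact time.** Let T = 1 for START and 0 for UC, and let D be contact time. If D = 0 whenever T = 0, then T x D = D for every patient. The linear predictor becomes

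b0 + bT T + bD D + bTD (T x D) = b0 + bT T + (bD + bTD) D.

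Only the sum bD + bTD enters the likelihood. Numerical check at 40 per arm, with gamma-distributed contact time in START (assumed):

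- The matrix [1, T, D, T x D] has rank 3 of 4, and the largest difference between D and T x D is 0. If D is missing in UC and only START rows remain, the rank is 2.
- The pairs (bD, bTD) = (0, -0.5), (-0.25, -0.25), (-0.5, 0) and (-5, 4.5) all sum to -0.5. At all four the log-likelihood is -58.362 for a linear outcome and -62.005 for a binary one.

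The horseshoe model still returns a posterior, and the data still inform the sum, which is the slope of outcome on contact time within START. The division between the two terms comes from the prior.

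Accidental UC contact does not rescue the term. With two contaminated UC patients (assumed) the rank is 4, but the SE of the interaction is 0.94 residual SD per unit of contact time. For a covariate present in both arms with the same assumed distribution it is 0.21. The estimate then rests on those two patients, and section 7.2 promises no measure of how much contact they had.

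**Step 3: total length of stay.** Total stay = days before randomisation + days after. Only the second part can be affected by START. A simulation with 80 patients, no true effect on outcome and no true moderation gave, for the interaction with total stay:

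- START does not affect the stay (assumed): about 0.01 days of use per day of stay.
- START shortens the stay by 1 day and halves its link with severity (assumed): about 0.
- START shortens the stay by 1 day and removes that link (assumed): -0.41.

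In the last two settings the START coefficient in that exploratory model was also off by about 1.4 to 1.6 days of use. With only pre-randomisation days it was about 0. The sizes follow from the assumptions; the dependence on START changing the stay does not.

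**Step 4: what a START-only report of contact time gives.** For a linear outcome the SE of the within-START slope, per SD of contact time, is 1/sqrt(n - 1) residual SD: 1/sqrt(39) = 0.160 with 40 patients and 1/sqrt(31) = 0.180 with 32. Without shared covariates the two-arm and START-only slopes agree exactly (-0.3709 in the linear check, 0.4140 in the logistic). With one baseline covariate shared across arms (assumed parameters), they differed by about 0.01 residual SD on average and the START-only intervals were about 2% wider.

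**The case against.** The strongest reply is that the plan labels this work exploratory, expects too little power, and says that significance is not the aim. The main comparison is untouched. The criticisms of contact time, total stay and inpatient diagnosis also depend on reading the reference as the 5.3 list. That reading is an inference, and the pain example in 7.1 does not settle it because PEG is in both places.

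Much of this is right, and it limits the point. But the literal Table 2 does no better, since it includes an item measured in START only, an in-hospital treatment that is itself an outcome, and 1-month scales. Spotting problem areas is one of the two goals that 7.1 sets for its models, so terms that cannot be interpreted matter for a stated purpose.

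A reader might also infer four stronger things that the documents do not support:

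- That total stay must bias the result. No section says that START changes the stay; the problem is conditional.
- That the model would fail to fit. The prior gives a posterior; what is lost is the meaning of the interaction.
- That the team will use 1-month pain. Section 5.3 lists PEG among baseline measures only, so baseline is the natural reading; the plan just does not say so.
- That contamination is ignored. Section 7.2 assesses whether and why it occurs; what is absent is its amount.

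**Conclusion.** The concern holds for the exploratory subgroup analysis. The table reference does not lead to a covariate list, and on either reading the rule in 7.1 admits moderators that are not fixed at randomisation. For contact time the defect is structural if UC contact is zero: rank 3 of 4, with no information in the data on the interaction. For total stay it depends on START altering the stay. For pain, inpatient diagnosis and insurance a stated time point is enough.

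A reader might go on to infer that the pilot's treatment estimates, or the variance carried into the future power calculation, are compromised. They are not: the main model contains none of these covariates beyond the baseline measure of the outcome. The change should be made, but the trial's main output does not depend on it.

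**What to change.** In section 7.1, replace the table reference with a named list of moderators, and state that every treatment interaction uses only values fixed before randomisation:

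- sociodemographics, and insurance at admission;
- ASSIST substance and severity from the eligibility screener;
- baseline PEG;
- the baseline scales already in Table 2 (PHQ-9, GAD-7, SIP-AD, stigma), which a bare pointer to the 5.3 list would drop;
- admission diagnosis, which is in the daily EPIC report;
- days from admission to randomisation in place of total stay, using the admission date and time in the same report.

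Remove contact time, all 1-month values and total stay as moderators. Report contact time against outcome within START only, labelled as a non-randomised comparison. This gives nearly the same slope as the two-arm fit, with slightly less precision when a baseline covariate is shared.

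The cost is SAP wording and possibly two dated fields in the data pull. Admission diagnosis is not in the monthly report list, which names only diagnoses during the encounter, and payer is in neither report list. Total stay and diagnoses made later in the stay are lost as exploratory moderators. No sample-size figure changes.
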